1.6 Oxidative Stress and ARDS

Oxidative stress is elevated with many disease states (Cracowski, 2000; Montuschi, 2000; Wood, 2000), and it is reasonable to postulate that levels of oxidative stress are even higher in illnesses representing more severe perturbations of the disease spectrum. In many critical illnesses, especially ones emanating from infection, macrophages are increased, recruited, and activated. The resultant increase in macrophage oxidative burst is vital in helping to overcome the inflammatory process. In addition, energy expenditure increases in critical illness. Studies have demonstrated that patients with sepsis and septic shock demonstrate elevated levels of oxidant stress (Goode, 1995; Gutteridge, 1999). Furthermore, the acute respiratory distress syndrome, a predominantly neutrophilic inflammatory process, also results in increased levels of oxidative

stress (Carpenter, 1998; Gutteridge, 1999; Schmidt, 2004). Some studies have suggested that levels of oxidative stress, as demonstrated by lipid peroxidation, correlate with worse outcomes in critically ill patients (Cowley, 1996). Studies of anti-oxidant therapy independently in patients with ARDS, however, are limited to trials investigating N-acetylcysteine (NAC). Despite demonstrating improved pulmonary physiology, three moderate-sized clinical trials investigating intravenous NAC failed to demonstrate any benefit in clinical outcomes, including no difference in 30-day or 60-day mortality, ventilator-free days, or ICU-free days (Bernard, 1997; Jepsen, 1992; Suter, 1994). Unfortunately, none of the studies measured changes in markers of oxidative stress. One study combining omega-3 fatty acid and anti-oxidant treatment, however, found normalization of low anti-oxidant levels, but no alteration in measures of oxidative stress (Bernard, 1997; Jepsen, 1992; Nelson, 2003; Suter, 1994).

1.7Caloric Restriction, Energy Expenditure, and Oxidative Stress

Trophic feedings, as utilized in this proposal, provide an enteral feeding regimen low in calories compared to full-calorie feedings. Caloric restriction (Koubova, 2003) delays the development of a wide spectrum of diseases, including kidney disease, neoplasias, diabetes, and autoimmune diseases, resulting in prolonged survival in multiple species (Fernandes, 1976; Jolly, 2005; Lane, 2001; Sohal, 1996). Although the mechanism of its action remains unknown it has been proposed that caloric restriction reduces oxidative damage generated by ROS produced during respiration (Afanas'ev, 2005; Heilbronn, 2006). Normally about 3% of oxygen consumed is converted to ROS by mitochondria; hence as energy expenditure increases, the ROS burden increases. Likewise, reducing energy expenditure decreases formation of radical generating molecules. Caloric restriction effectively decreases energy expenditure (Heilbronn, 2006), and has been shown to decrease the production of ROS, resulting in less oxidative stress in animal models (Yu, 2005). We hypothesize that caloric restriction and decreasing inflammation through administration of trophic feedings will result in lower levels of oxidative stress.

1.8 Measurement of Long Term Outcomes and Acute Lung Injury

Emerging data indicate that survivors of acute lung injury have substantial disability after recovery from acute lung injury. After hospital discharge, only about one-third return to home and more than one-half reside in skilled nursing facilities or rehabilitation facilities (Rubenfeld, 2005). Up to one year later, most patients have serious deficits in health-related quality of life, functional performance, cognition, and employment (Herridge, 2003; Hopkins, 2005). Mortality and ventilator-free days, which have been the primary outcomes in most clinical trials of treatments for acute lung injury, do not capture these important longer-term decrements (Brower, 2004; Schoenfeld, 2002; The Acute Respiratory Distress Syndrome Network, 2000). Moreover, it has recently become clear that acute lung injury, contrary to previous belief, becomes a chronic, disabling pulmonary condition in many cases (Herridge, 2003). To capture the full impact of any treatment for acute lung injury, longer term outcomes must be assessed.

The effects of treatment for acute lung injury on short term mortality may not capture the full impact of treatment over the longer term. A treatment may have early benefit that is maintained, amplified, or attenuated over a longer time period. For example, an invasive strategy for diagnosing ventilator-associated pneumonia reduced 14 day mortality, but the benefit decreased thereafter and the mortality benefit was lost (Fagon, 2000). In addition, a treatment may improve

mortality but have additional deleterious effects that adversely affect long term outcomes such as health-related quality of life and functional performance. For example, parenteral corticosteroids, which may have some immediate benefit in late-phase ARDS, may have detrimental longer-term effects on muscle function and weakness that lead to impaired physical functioning (Herridge, 2003; Steinberg, 2006). To fully evaluate new therapies for acute lung injury, a broad spectrum of long term outcomes must be ascertained. Moreover, measurement of long-term outcomes is necessary to compare the cost-effectiveness of different strategies for ARDS (Angus, 2001).

2 Objectives

2.1 Primary Objectives

• Evaluate the efficacy and safety of initial trophic enteral feeds followed by advancement to full-calorie enteral feeding vs. initial advancement to full-calorie enteral feeding management strategies on mortality, ventilator-free days, ICU-free days, and organ failure in patients with Acute Lung Injury or Acute Respiratory Distress Syndrome

2.2 Secondary Objectives

To develop and analyze a clinical database of patients enrolled in the clinical trial who are well characterized and followed for 12 months for the purpose of answering questions about the natural history of ARDS and evaluating the effect of different interventions a and patterns of supportive care.

2.3 Primary Hypotheses

• Initial trophic feeding followed by full-calorie enteral feeding will increase the number of ventilator-free days to study day 28 in patients with ALI or ARDS by reducing systemic inflammation and the number of feeding complications as compared to early, full-calorie enteral feeding.

2.4 Secondary Hypotheses

- The timing of advancing enteral feeds to full feeding rates will alter plasma IL-6 and IL-8 levels in patients with ALI or ARDS compared to early, full-calorie enteral feeding.
- Initial trophic feeding followed by full-calorie enteral feeding will decrease the incidence of gastrointestinal intolerances (vomiting, aspiration, regurgitation, diarrhea, elevated gastric residual volumes, and abdominal distention and cramping) compared to early, full-calorie enteral feeding.
- Initial trophic feeding followed by full-calorie enteral feeding will decrease the incidence
 of ventilator-associated pneumonia in patients with ALI or ARDS compared to early,
 full-calorie enteral feeding.
- Initial trophic feeding followed by full-calorie enteral feeding will decrease the incidence
 of developing bacteremia in patients with ALI or ARDS compared to early, full-calorie
 enteral feeding.

3 End Points

Analysis of primary and all secondary endpoints will be conducted on an intention to treat basis. A secondary analysis will be performed looking at patients who achieved greater than 70% of full-calorie feeds for the initial 6 days.

3.1 Primary Endpoint

1. Ventilator-Free Days to study day 28

VFDs is a composite endpoint that is affected by mortality and duration of mechanical ventilation in survivors (Schoenfeld, 2002), which has been chosen as the primary endpoint for a number of reasons. VFDs provide a validated measure of improved lung function, even if overall mortality is only minimally altered. In addition to also possibly altering inflammation, full-calorie feedings may place patients at risk for aspiration, which may result in increased mortality, but will result in fewer ventilator-free days, even in non-fatal cases. Further, VFDs is a measure of a morbidity outcome and it is directly related to "days of assisted ventilation." However, a trend in one treatment group toward early patient death would likely decrease the number of days of assisted ventilation. This example of decreased days of assisted ventilation is misleading as the treatment group actually had a worse outcome. Measuring ventilator days in survivors would offset the problem of early mortality decreasing ventilator days. However, if a treatment group had a favorable trend towards improved survival, but required additional ventilator days for survival, "average number of ventilator days in survivors" could also be misleading. VFDs represent a measurable outcome that is favorably affected by both shorter duration of assisted ventilation in survivors and lower mortality.

VFD to day 28 is defined as the number of days from the time of initiating unassisted breathing to day 28 after randomization, assuming survival for at least two consecutive calendar days after initiating unassisted breathing and remains free of assisted breathing to day 28. If a patient returns to assisted breathing and subsequently achieves unassisted breathing to day 28, VFD will be counted from the end of the last period of assisted breathing to day 28 unless a period of assisted breathing was less than 24 hours and the purpose of assisted breathing was a surgical procedure. If a patient was receiving assisted breathing at day 27 or dies prior to day 28, VFD will be zero. Patients transferred to another hospital or other health care facility prior to day 28 while still receiving assisted breathing will be followed to assess this efficacy measure. Unassisted breathing is defined as breathing with facemask or nasal prong oxygen (or room air) following extubation, T-tube breathing, breathing with continuous positive airway pressure (CPAP \leq 5 cm H₂O without PS or IMV assistance), or tracheotomy mask breathing.

3.2 Secondary Endpoints

1. The secondary efficacy variable for the trial is mortality prior to hospital discharge with unassisted breathing. Patients alive in hospital at day 60 will be considered to have survived.

- 2. Mortality before hospital discharge home, with unassisted breathing, to day 90. Patients alive in hospital to day 90 will considered to have survived
- 3. Number of ICU-free days at 28 days after randomization
- 4. Number of organ failure-free days at 28 days after randomization. Organ failure will be defined by previously validated definitions for renal, circulation, central nervous system, hematologic, and hepatic organ and system failures (Bernard, 1997).

Organ failure is defined as present on any date when the most abnormal vital signs or clinically available lab value meets the definition of clinically significant organ failure according to the Brussels Organ Failure Table. Patients will be followed for development of organ failures to death, hospital discharge or study day 28, whichever comes first. Each day a patient is alive and free of a given clinically significant organ failure will be scored as a failure-free day. Any day that a patient is alive and free of all 5 organ failures will represent days alive and free of all organ failure. Central nervous system dysfunction is evaluated using the Glasgow Coma Scale.

- 5. Number of days between the day of first meeting criteria for weaning-readiness (see Appendix G, section G.2.) and day 28 after randomization.
- 6. Mortality and VFDs in patients with pre-randomization $PaO_2/F_1O_2 \le 200$.
- 7. Change in plasma levels of IL-6, IL-8, VWF, SPD, and total protein concentrations from baseline to study day 3.
- 8. Ventilator free days and mortality prior to hospital discharge with unassisted breathing to day 60 and number of ventilator-free days to day 28 in patients with shock (defined in 2.1.2) at the time of randomization.

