3.3 Other Endpoints

Many of these proposed outcomes are not meant to definitively establish the underlying mechanisms, but instead will explore biochemical endpoints to provide additional support or generate other hypotheses of how the interventions may result in different clinical outcomes.

- 1. Increase of PaO₂ / FiO₂ ratio on study days 1-7
- 2. Improvement in Lung Injury Score on study days 1-7
- 3. Number of gastrointestinal intolerances (aspiration, vomiting, regurgitation, diarrhea, elevated gastric residual volumes, abdominal distention and cramping) on study days 1-7
- 4. Level of systemic inflammation, as measured by plasma IL-6 and IL-8 levels.

5.

- 6. Measure of oxidative stress on days 3, 6 and 12 compared to baseline as measured by urinary levels of F₂-isoprostane metabolites
- 7. Incidence of bacteremia.
- 8. Incidence of Clostridium dificile induced diarrhea.
- 9. Incidence of ventilator-associated pneumonia
- 10. Serum levels of markers of nutrition, including albumin and total protein levels between baseline and days 6 and 12.

Clostridium dificile diarrhea will be diagnosed by one or more daily stool specimen positive for cytotoxin assay or enzyme immunoassay. Patients with more than 3 liquid stools totaling more than an estimated 500 ml of stool per day, or those with systemic inflammatory response

syndrome unexplained by other infection, may have up to three daily stool samples sent for *C. difficile* investigation (either cytotoxin assay or enzyme immunoassay).

Bacteremia will only be considered if it develops greater than 24 hours after the initiation of study procedures and is documented with a positive blood culture. The primary medical team, using clinical judgment, will determine when blood cultures are sent. Coagulase negative (or thermo nuclease negative) *Staphylococci* or *Corynebacterium* bacteremia require the isolation of these organisms from at least two blood cultures drawn within 24 hours of each other containing the same organism in order to be deemed significant.

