 - (b) Worst systolic blood pressure for that date
 - (c) Worst creatinine, bilirubin, and platelet count for the date
 - (d) Use of vasopressors
 - (e) Glasgow Coma Score

- 12. Blood for cytokines, mediators, and markers of inflammation. Plasma obtained from two, 10 ml EDTA anti-coagulated blood samples will be divided immediately after centrifugation into 4 equal 2 ml aliquots in specified tubes and frozen at -70^oC. Blood will be collected on days 0, 3, 6, and 12.
- 13. Urine for isoprostane metabolites. Urine obtained from the patients will be collected in an 8 ml sample tubes and divided into 4 aliquots of 2 ml each in specified tubes and frozen at -70°C. Urine will be collected on days 0, 3 and 6
- 14. Enteral feeding volume and number of calories received for the previous 24 hours.
- 15. Number and type of gastrointestinal intolerances for the previous 24 hours.
- 16. Episodes of VAP
- 17. Episodes of bacteremia
- 18. Episodes of Clostridium dificile-induced diarrhea

Samples will be sent to a central repository to be stored (as described below). Samples will be identified by random number during shipment and storage in the central repository. In the future, when approved studies are received at the CCC the CCC will instruct the repository to prepare the appropriate samples for shipment. The key relating the ARDSNet study number to the new specimen number will be kept at the CCC in a locked file. The CCC does not record or store unique patient identifiers (such as initials, date of birth, hospital record numbers, addresses, phone numbers, etc.) in the database. All data released by the CCC for studies will be linked to the specimen but will be de-identified. The link (key) between the de-identified database and the patient will be removed two years after the primary publication.

Note: Urine and plasma collected for this trial will be frozen and stored at a Bio repository for future research.

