Mortality will be compared at interim data analyses using Kaplan Meier estimates at 60 days and their associated standard errors. This analysis will be stratified as above and a test for interaction of treatment with strata will be presented. At the end of the study sixty-day mortality will be compared using a Mantel-Haenzel test as long as all patients can be followed. If not the method used for the interim analyses will be used.

Other Endpoints

The number of ICU-free days, Organ-Failure Free days, and days from first weaning readiness will be analyzed in the same manner as is described above for the primary endpoint. In addition we will test for interactions between treatment and gender and race as per NIH guidelines (National Institutes of Health, 2001).

Changes in plasma levels of IL-6, IL-8, and protein will be compared in two analyses. An analysis of covariance will test for a treatment effect on the day 3 value of these variables using the day 0 value as a covariate. In addition, a multivariate analysis of variance will test for a baseline difference between day 3 and day 0.

Table 3 illustrates the detectable differences for endpoints, assuming 1000 patients enrolled, 90% power, and a two-sided alpha-level of 0.05.

Table 3: Detectable Differences for Secondary Endpoints

Variable	Incidence or Mean	Standard Deviation	Detectable Difference
PaO ₂ / FiO ₂	155	73	15
ICU free days	13.4 days	12.6 days	2.6 days
Shock free days	19.1 days	4.93 days	2.23 days
Plasma IL-6 (pg/ml)	1252	862	177
Plasma IL-8 (pg/ml)	149	93	19
28 day hospital mortality	22%		8.2%
90 day hospital mortality	25.4%		8.6%

Changes in physiologic lung indices on days 1-7 will be compared using a multivariate analysis of variance.

Twice during the early part of the study, the DSMB will evaluate the glucose control between the trophic and full-calorie arms to ensure that the levels of blood glucose are not clinically different between the groups over the first 6 days of the study. These evaluations will occur after approximately 100 and 250 patients are enrolled in the study. Should the blood glucose values differ between the groups at these evaluations, the guidelines for controlling blood glucose levels for the remainder of the study may be adjusted in an attempt to equalize the blood glucose levels for the study.

8 Data Collection and Site Monitoring

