- b. Guillain-Barré Syndrome
- c. Myasthenia gravis
- d. Upper spinal cord injury at level C5 or above
- e. Kyphoscoliosis or chest wall deformity resulting in severe exercise restriction (unable to climb stairs or perform household duties), secondary polycythemia, or respirator dependence

5. Severe Chronic Respiratory Disease

[figure not shown]
Any of the following is considered severe chronic respiratory disease and excludes a patient from being eligible for enrollment:

- 1. FEV₁ less than 20 ml/kg PBW (e.g. 1.4 L for a 70 kg person), or
- 2. FEV₁/VC less than 50% predicted, or
- 3. Chronic hypercapnia (PaCO₂ greater than 45 mmHg) and/or chronic hypoxemia (PaO₂ less than 55 mmHg) on $F_1O_2 = 0.21$, or
- 4. Radiographic x-ray evidence of any chronic over-inflation or chronic interstitial infiltration, or
- 5. Hospitalization within the past six months for respiratory failure in patients with chronic respiratory disease. (PaCO₂ greater than 50 mmHg or PaO₂ less than 55 mmHg or O₂-Sat < 88% on FiO₂ = .21).
- 6. Chronic restrictive, obstructive, neuromuscular, chest wall or pulmonary vascular disease resulting in severe exercise restriction, e.g., unable to climb stairs or perform household duties, secondary polycythemia, severe pulmonary hypertension (mean PAP greater than 40 mmHg), or respirator dependency.

C Trophic Feeding Protocol

D Full-calorie Feeding Protocol

Time-Events Schedule \mathbf{E}

Measurement/Event	Day 0	1	2	3	4	5	6	7	8	9	10	11	12	14	21	28	60
Demographics, History & Physical, Height, Weight	X																
Etiology of ARDS, site of sepsis if septic etiology	Х																
APACHE III Score ^C	Х																
HCG (in females)	Х																
Vital Signs (HR, SBP, DBP, Temp °C) *	Х	Х	Х	Х	Х	Х	Х	Х	Х	Х	Х						
Central Venous Pressure *	Α	Α	Α	Α	Α	Α	Α	Α	Α	Α	Α						
Fluids (In and Out) *	Х	Х	Х	Х	Х	Х	Х	Х									
Brussels Score ^B ~	Х	Х	Х	Х	Х	Х	Х	Х	Х	Х	Х	Х	Х	Х	Х	Х	
Glasgow Coma Scale	Х							Х								X**	
Ventilator Parameters (including FiO ₂) *#	Х	Х	Х	Х	Х		Х						Х		Х	Х	
Arterial Blood Gases (PaO ₂ , PaCO ₂ , pH) and SpO ₂	Х	Α	Α	Α	Α		Α						Α		Α	Α	
Serum Glucose, Na+, K+, HCO3-, Hgb	Х	Α	Α	Α	Α	Α	Α	Α	Α	Α	Α	Α	Α				
Creatinine, Platelets, Bilirubin, BUN Hct,	Х																
Chest X-ray (# quadrants for lung injury score)	Α	Α	Α	Α	Α	Α	Α	Α	Α	Α	Α						
Record Sedatives, narcotics, pressors * (Y/N)	Х	Х	Х	Х	Х	Х	Х	Х	Х	Х	Х	Х	Х				

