Serum magnesium and phosphorus	Х	Х	Α	Х	Α	Α	Α	Α	Х	Α	Α	Α	Α				
Total Protein and Albumin	Х	Х	Α	Α	Α	Α	Α	Х	Α	Α	Α	Α	Х				
Ventilator–Associated Pneumonia assessment ^v	Α	Α	Α	Α	Α	Α	Α	Α	Α	Α	Α	Α	Α	Α	Α	Α	
Insulin dose at time of glucose level	Α	Α	Α	Α	Α	Α	Α	Α	Α	Α	Α	Α	Α				
Location of Feeding tube (e.g., gastric, post-pyloric) *	Х	Α	Α	Α	Α	Α	Α	Α	Α	Α	Α	Α	Α				
Volume of tube feeds / Calories delivered *		Х	Х	Х	Х	Х	Х	Х	Х	Х	Х	Х	Х				
Number and type of Gastrointestinal Intolerances		Х	Х	Х	Х	Х	Х	Х	Х	Х	Х	Х	Х				
Pro-kinetic agents, anti-diarrheals, anti-emetics * (Y/N)	Х	Х	Х	Х	Х	Х	Х	Х	Х	Х	Х	Х	Х				
Prothrombin Time	Α	Α	Α	Α	Α	Α	Α	Α	Α	Α	Α	Α	Α				
Plasma for Cytokines IL-6 and IL-8	Х			Х			Х						Х				
Urine isoprostane metabolites	Х			Х			Х										
Whole blood for DNA	Х																
Episode of bacteremia (record positive blood cultures) *		Α	Α	Α	Α	Α	Α	Α	Α	Α	Α	Α	Α	Α			
Clostridium dificile diarrhea tests		Α	Α	Α	Α	Α	Α	Α	Α	Α	Α	Α	Α	Α			
Vital Status §																Х	Х

A=When available

 $^{^{\}text{C}}=$ Labs not available in the 24 hours before randomization must be obtained

V = VAP assessment from available CXR, sputum culture, gram stain and WBC until extubated or day 28, whichever occurs first *= Data gathered at times indicated or until 48 hours UAB, whichever occurs first **=On day 28 or hospital discharge dates.

B=Records clinically available creatinine, platelets, bilirubin, SBP and vasopressor use

^{~=}Data gathered on days 0-28 or until d/c from study hospital

^{#=}Measure during reference period (0600-1000); other values may be obtained closest to 0800 on the specified calendar date §=Measure at 90 days and 12 months as part of Long Term outcome.

F Adverse Events

1. Procedures for Reporting Adverse Events

Assuring patient safety is an essential component of this protocol. Each participating investigator has primary responsibility for the safety of the individual participants under his or her care. The Principal Investigator will evaluate all adverse events. The Study Coordinator must view patient records for possible adverse events throughout the study period. All adverse events occurring within the study period must be reported in the participants' case report forms.

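### The protocol contradicts itself on whether the daily Glasgow Coma Score behind organ-failure-free days is collected, and the PaO2/FiO2 and isoprostane endpoints name days that the schedule leaves blank

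*Protocol*

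**What the plan says.** **Organ-failure-free days.** Section 3.2 item 4 covers renal, circulatory, CNS, hematologic and hepatic failure. The rule works by date: "Organ failure is defined as present on any date when the most abnormal vital signs or clinically available lab value meets the definition". Follow-up for this purpose ends at death, hospital discharge or day 28. The composite is defined by "Any day that a patient is alive and free of all 5 organ failures will represent days alive and free of all organ failure", and "Central nervous system dysfunction is evaluated using the Glasgow Coma Scale".

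**What is recorded, and when.** Section 6.3 says variables are recorded on the days shown in Appendix E. Its item 11 lists the Brussels data, which include (a) the worst PaO2/FiO2 of the date and (e) the Glasgow Coma Score. In Appendix E the Brussels row is gathered on days 0-28 or until discharge, but its content footnote reads "Records clinically available creatinine, platelets, bilirubin, SBP and vasopressor use". A separate row, "Glasgow Coma Scale", is marked on day 0, day 7 and day 28, the last footnoted as day 28 or discharge.

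**PaO2/FiO2.** Section 3.3 item 1 makes this an endpoint on days 1-7. Section 7 adds: "Changes in physiologic lung indices on days 1-7 will be compared using a multivariate analysis of variance".

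**Isoprostanes.** Section 3.3 item 6 is a "Measure of oxidative stress on days 3, 6 and 12 compared to baseline", using urinary metabolites. Section 6.3 item 13 says: "Urine will be collected on days 0, 3 and 6".

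**The concern.** Organ-failure-free days are a named secondary efficacy variable in the Study Summary, where CNS is listed explicitly. Organ failure is also part of the primary objective in section 2.1, and section 7 analyses these days in the same way as the primary endpoint. A day can count as free of all organ failure only if CNS status is known on that day. Sites that follow Appendix E would not record GCS daily, and the five-organ count would then have an unknown component on most days. Whatever is done with the unknown days changes the endpoint. Scoring them as failure-free, for example, would credit sedated or comatose survivors with days they may not have earned.

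For PaO2/FiO2, the days analysed and the days scheduled disagree. An analysis needing a full set of days also loses patients through death or early liberation from the ventilator, which is the outcome the trial is testing. For isoprostanes, one of the named days has no sample behind it.

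**Working it through.** The plan gives no figure to reproduce here. The check compares the days each endpoint needs with the days the schedule provides. The Appendix E header has 17 days (0-12, 14, 21, 28, 60), and each row used below has 17 cells.

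| Appendix E row | Days marked | Days the endpoint needs |
|---|---|---|
| GCS | 0, 7, 28 or discharge | every day to death, discharge or 28 |
| Brussels data (footnote omits GCS and PaO2/FiO2) | 0-28 | every day to death, discharge or 28 |
| Ventilator parameters, including FiO2 | 0-4, 6, 12, 21, 28 | 1-7 |
| Arterial blood gases (when available after day 0) | 0-4, 6, 12, 21, 28 | 1-7 |
| Urine isoprostanes | 0, 3, 6 | 3, 6, 12 against baseline |

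1. **GCS.** Take a patient in hospital through day 28. Follow-up days 1 to 28 number 28. Days with a scheduled GCS are 7 and 28, so 2. Days without are 28 - 2 = 26. For a patient discharged alive on day d, after day 7 and before day 28, scheduled values fall on day 7 and the discharge date, so d - 2 of d days have none. With d = 14 that is 12 of 14.

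2. **The other organs.** The Brussels footnote supplies creatinine (renal), bilirubin (hepatic), platelets (hematologic), and systolic pressure with vasopressor use (circulatory). These four counts have a daily input. The missing input is the CNS one, and it affects the CNS count and the five-organ count.

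3. **Section 6.3 against Appendix E.** Item 11(e) puts GCS in the Brussels data, and the Brussels row is daily. Read alone, that means daily GCS. The footnote to that row leaves GCS out, and Appendix E gives GCS its own sparse row, which would have no purpose if GCS were already daily. Both readings have text behind them.

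4. **PaO2/FiO2.** Of the 7 endpoint days, days 1, 2, 3, 4 and 6 are scheduled, which is 5. Days 5 and 7 are blank in both the blood-gas and the ventilator rows. Item 11(a) would supply a worst PaO2/FiO2 on every date, but the Brussels footnote omits that too. The two sources also measure different things: the reference values in section 6.3 are those closest to 8:00 A.M., while item 11(a) is the worst of the day. Filling days 5 and 7 from item 11(a) would mix them. In addition, the ventilator row stops at 48 hours of unassisted breathing, so complete vectors come mainly from patients still ventilated.

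5. **Isoprostanes.** Of the 3 post-baseline days named, days 3 and 6 are sampled and day 12 is not. Section 6.3 and Appendix E agree on this, and nothing else in the protocol provides a day-12 urine sample. The plasma row does include day 12; the urine row does not.

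**The case against.** The strongest reply is that section 6.3 item 11 already lists both GCS and worst PaO2/FiO2 as Brussels data, on a row gathered daily to day 28. On that reading the inputs exist and the footnote is merely incomplete. This stands far enough to rule out several stronger conclusions that a reader might draw.

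- **That organ-failure-free days cannot be computed.** The documents show two conflicting instructions, not a settled absence. Four of the five organ-specific counts are intact either way.
- **That no patient can have a complete PaO2/FiO2 vector for days 1-7.** This follows from the blood-gas and ventilator rows alone. It fails if item 11(a) was collected daily.
- **That Lung Injury Score is unsampled on days 5 and 7.** The protocol describes collection of this score only by counting chest radiograph quadrants, and that row is marked when available on every day from 0 to 10. Saying the score also needs gases and ventilator settings would rest on a definition the protocol does not give.
- **That unknown CNS days will be scored as failure-free.** No section says so. How missing days are handled may properly sit in the statistical analysis plan, which is not at hand.

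It can also be said that 26 of 28 applies only to patients in hospital through day 28. That is correct, and the figure is stated with that condition.

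The reply does not remove the contradiction. Section 6.3 itself hands the choice of recording days to Appendix E, and Appendix E excludes GCS from the daily record. An analysis plan can set rules for missing values, but it cannot supply observations that the schedule did not ask sites to make.

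**Conclusion.** The point holds as a contradiction between the endpoint definitions, section 6.3 and Appendix E. The CNS and five-organ failure-free-day counts depend on a daily GCS that section 6.3 lists and Appendix E does not schedule. On the Appendix E reading, 26 of 28 follow-up days lack a scheduled GCS for a patient in hospital through day 28. PaO2/FiO2 has a similar conflict on 2 of its 7 days. Day-12 isoprostane is the only item that is simply unavailable; days 3 and 6 remain usable.

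This rests on Appendix E governing recording days, as section 6.3 says, and on the row marks lining up with the header days. What the case report form actually captured is not shown and would settle the practical size of the problem. The matter is worth correcting because it reaches a named secondary efficacy variable. It does not affect ventilator-free days, the sample size or the stopping boundaries.

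**What to change.** 1. Reconcile section 3.2 item 4, section 6.3 item 11, the GCS row and the Brussels footnote by adding clinically available GCS and worst PaO2/FiO2 to the daily Brussels record.
2. Check what was captured for patients already enrolled (section 4.1 refers to the first 272). If daily GCS was not recorded for them, report a four-organ count alongside the five-organ one and show CNS separately. Do not score unknown CNS status as failure-free. Removing CNS from the endpoint outright would go further than the evidence requires.
3. State which PaO2/FiO2 measure the endpoint uses (reference value or worst of the date) and on which days. Analyse it with a repeated-measures mixed model adjusted for the day-0 value, which keeps patients with incomplete vectors, in place of a MANOVA that needs every day.
4. Delete day 12 from the isoprostane endpoint in section 3.3.

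The cost is wording changes, one change of model and possibly one case-report field. Patients already past the relevant days cannot be given values that were never recorded, so the four-organ count may have to carry part of the reporting.
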